Data collection procedures

Participants from *Sing-a-Lung 1.0* have already provided written consent for a long-term follow-up contact. All participants will therefore be contacted directly by telephone by the research assistant Department of Medicine, Hospital Lillebaelt, Vejle, during February to May 2023 and asked for their consent to participate in the follow-up study. The research assistant will collect data by telephone and data will be entered directly into web-based, software survey tool and secure database, SurveyXact by Ramboll (Rambøll Management Consulting, Aarhus, Denmark)¹⁰ which will be used for survey distribution, data collection, and data storage. PostDoc, Ph.d., [name], is in charge of the overall data collection.

Data analysis procedures

In June 2023, data will be transferred from the database at SurveyXact by Ramboll to Microsoft Excel file and imported into statistical software STATA 17 (StataCorp LLC, Texas, USA). Data will be anonymised, cleaned and prepared (see section: Analysis plans/Modifications of specific variables of interest to be included in the logistic regression models) before merging with the original dataset and related 1:1 to observations from *Sing-a-Lung 1.0*. Merging and subsequent analysis process will start July 2023.

Variables

Measured variables

For the long-term follow-up study, data collection includes current smoking status, and patient-reported health care utilisation, exacerbations, and usage of COPD-related medicine since *Sing-a-Lung 1.0*. Besides, the data collection includes patient-reported knowledge on availability of local structured or unstructured offer of singing, for example a lung choir, and on availability of local structured or unstructured offer of physical training after the intervention.

Furthermore, we will collect data related to the following outcomes and variables of interest:

Study outcomes	Measure
Primary study outcome	
1. Long-term upkeep of activity	
Participation in local, structured or unstructured singing activity, for example a lung choir.Participation in local, structured or unstructured upkeep course in physical training.Participation in any other activity (physical, musical, or creative).Overall self-evaluated level of physical and social activity compared to before intervention.
Secondary study outcomes	

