2. Long-term sustaining of effect - QoL, anxiety, depression, dyspnoea, etc.	
QoL: St. George's Respiratory Questionnaire (SGRQ)Anxiety and depression: (Hospital Anxiety and Depression Scale (HADS))Dyspnoea: modified Medical Research Council (mMRC) (dyspnoea scale)
3. Self-reported satisfaction with intervention, experience of relevance, and experienced integration of tools obtained during Sing-a-Lung 1.0	
Satisfaction with the interventionExperience of overall relevance of content of the interventionUse and integration of tools obtained during intervention

Analysis Plan

Statistical models

Overall

Quantitative data from validated questionnaires will be analysed using standard calculators and cut-off for minimal important differences developed for the specific tools,¹¹⁻¹⁵ In lack of a formal, absolute tool for survey research analysis,^{16,17} we will use a conventional approach to analyse quantitative and semi-quantitative data from the specially developed questionnaires. Hence, categorial data will be described with number and percentage (categorical data) and continuous data with either mean +/- standard deviation (normally distributed continuous data) or median and range (not normally distributed continuous data).

Differences in within-groups and between-groups effects will be investigated with relevant test for continuous data (independent samples, paired-samples, related-samples, and repeated-measures) and categorical data (Chi² or Fischer's test). Adjusted and unadjusted univariable and multivariable logistic regression models will be included to analyse relevant correlations. Furthermore, we will explore any potential interactions.

Baseline characteristics will be explored in the following primary and supplementary analyses: Characteristics and performance in 1) Overall total study population (baseline, short-term follow-up, and long-term follow-up), 2) Included, not accepting/not reachable, deceased, 3) Deceased (low, medium, high RCT adherence), 4) RCT randomisation (SLH, PExT).

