Modifications of specific variables for analyses: 1) Adherence during RCT (ranging from 0 to 20 sessions attended; classified into three categories: zero: 0%; low: 1-49%; medium: 50-74%; high: 75-100%), 2) Intervention randomisation, 3) Sustaining of effects: QoL, anxiety, depression, dyspnoea or not (all related to minimal important difference, MID (4 units for SGRQ and 1 for HADS and mMRC), 4) Achievement of MID in RCT (SGRQ and 6MWD) or not, 5) Age categorised into quartiles, 5) FEV1% predicted categorised according to GOLD (1-4),^{6,8} 6) Baseline 6MWD categorised into quartiles, 7) Available offer of singing/physical training or not.

STROBE Statement checklist for cohort studies will be used for reporting. Statistical analyses will be performed using statistical software STATA 17 (StataCorp LLC, Texas, USA). Statistical significance will be reported as $p < 0.05$.

Ethics

Written consent for long-term follow-up contact was provided in *Sing-a-Lung 1.0* and as the long-term-follow-up study, moreover, will be solely questionnaire-based, ethical approval from The Committee on Health Research Ethics was not required. The study was approved by The Danish Act on Processing of Personal Data regarding re-accesses to the raw data of *Sing-a-Lung 1.0* in order to retrieve patients' contact information and to conduct the new questionnaire-based study of the long-term-follow-up study (REG-135-2022).

Feasibility

The long-term follow-up study will be managed and facilitated by PostDoc, Ph.d., [name]. The study will be conducted at Pulmonary Research Unit Zealand (PLUZ), Zealand University Hospital Roskilde and Naestved Hospital. Furthermore, Medical and Respiratory Department, Hospital Lillebaelt, Vejle, will participate with academic qualification and advice and will donate salary for the research assistant responsible for data collection.

Funding

Funding has been obtained from the following funding bodies: The Danish Health Foundation (DKK 200.000), The Danish Lung Foundation (DKK 100.000), Region Zealand Chiesi Pharma AB (DKK 85.000). The research assistant responsible for data collection was employed and paid by Hospital Lillebaelt.

Dissemination

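### Age, FEV1% predicted and baseline 6MWD are planned as four-class variables in the logistic models; continuous terms would adjust slightly better with fewer parameters

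*SAP*

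**What the plan says.** In the SAP's Analysis Plan, the paragraph on modifications of specific variables fixes the coding of three baseline measurements: "5) Age categorised into quartiles" and "6) Baseline 6MWD categorised into quartiles", while FEV1% predicted goes into the four GOLD classes ("5) FEV1% predicted categorised according to GOLD (1-4").

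This coding is not only for description. The Data analysis procedures section refers to the list as "Modifications of specific variables of interest to be included in the logistic regression models". The Statistical models section then states: "Adjusted and unadjusted univariable and multivariable logistic regression models will be included to analyse relevant correlations". It adds: "Furthermore, we will explore any potential interactions".

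No section plans a continuous or spline form for these three variables, and none says which of the listed variables enter which model.

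**The concern.** Age, lung function and walking capacity can plausibly influence both how many sessions a participant attended and whether activity was kept up years later. Attendance was not randomised, so the primary hypothesis linking adherence to upkeep depends on adjustment for such variables.

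Four classes treat everyone within a class as alike, so differences inside the class go unadjusted. They also use three coefficients where a linear term uses one. The sample is at most 270, less those who decline, cannot be reached or have died, and the number of people with upkeep is unknown. At stake are some precision and some confounding control in the adherence analysis, and likewise in the analyses of MID achievement and of available local offers.

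**Working it through.** **Inputs from the SAP.** Age, 4 classes. FEV1% predicted, 4 classes. Baseline 6MWD, 4 classes. Arm, 2 levels. Adherence, "classified into three categories: zero: 0%; low: 1-49%; medium: 50-74%; high: 75-100" per cent: four levels are listed although the text says three, so 3 parameters (2 if two levels are merged). Cohort: 145 + 125 = 270, which reproduces the SAP's figure. The SAP gives no respondent number, upkeep rate or parameter count to reproduce.

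**Assumed.** Respondents and upkeep rate, shown at two points: 270 with 50% (the ceiling) and 150 with 30%.

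**Step 1: parameters for the three covariates.** Indicator coding costs (classes - 1) each.
- Categorised: 3 x (4 - 1) = 9, if all four GOLD classes are occupied.
- Linear: 3 x 1 = 3.
- Restricted cubic splines, 3 knots: 3 x 2 = 6.

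**Step 2: illustrative adjusted model.** Arm (1) + adherence (3) + the three covariates. Events = respondents x upkeep rate.

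| Coding | Parameters | 270 x 0.50 = 135 events | 150 x 0.30 = 45 events |
|---|---|---|---|
| Categorised | 1 + 3 + 9 = 13 | 135/13 = 10.4 | 45/13 = 3.5 |
| 3-knot splines | 1 + 3 + 6 = 10 | 135/10 = 13.5 | 45/10 = 4.5 |
| Linear | 1 + 3 + 3 = 7 | 135/7 = 19.3 | 45/7 = 6.4 |

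Interactions widen the gap. Arm by a four-class covariate costs 1 x 3 = 3 parameters, against 1 for a linear term.

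**Step 3: information kept by quartiles (age, 6MWD).** For a standard normal covariate the quartile means are about -1.271, -0.325, 0.325 and 1.271. The between-class variance is 0.25 x 2 x (1.271² + 0.325²) = 0.86. So about 86% of the variance is kept and 14% is lost.

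**Step 4: confounding left after quartile adjustment.** This was simulated with 1,000,000 observations, one normal confounder with a linear effect on the log-odds of both exposure and outcome, and no true exposure effect.

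| Confounder coefficient (exposure and outcome) | OR unadjusted | OR quartile-adjusted | OR linear-adjusted | Share of log OR left by quartiles |
|---|---|---|---|---|
| 0.5 | 1.25 | 1.03 | 1.00 | 13% |
| 1.0 | 2.02 | 1.09 | 1.00 | 12% |

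About one eighth of the confounding by that variable remains.

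**The case against.** The coding is prespecified, easy to read and internally consistent. GOLD classes are a recognised clinical convention. Quartiles also guard against wrongly assuming linearity, and the simulation generates a linear effect, so it favours the linear term by construction. The residual bias is small even so: an odds ratio of 1.03 or 1.09 where the truth is 1.00. The SAP does not call these variables confounders and gives no data on how strongly they relate to adherence or upkeep. All of this stands, and it limits the point to a modest one.

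It does not remove it. A 3-knot spline relaxes linearity and still uses 6 parameters rather than 9. The convention argument supports GOLD classes in tables, not as the adjustment term.

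Three stronger readings are tempting, and the SAP does not support them:
- A reader might put every listed variable into one model and count about 21 parameters. Four of those would be the sustained-effect items, which the SAP lists among its outcomes, and no section places all the variables in one model.
- A reader might apply the 14% loss to all three covariates. It is a result for quartiles of a normal variable and does not carry over to GOLD classes.
- A reader might say that all the cut-points depend on the sample. That is true of the quartiles only; GOLD is an external classification.

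**Conclusion.** The point holds as a minor weakness of method. The planned coding uses up to 9 parameters where 3 (linear) or 6 (3-knot splines) would do. For age and 6MWD it leaves about one eighth of the confounding by that variable, if the variable is near normal and its effect near linear on the log-odds scale.

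The 9 assumes indicator coding with all GOLD classes occupied. The events-per-parameter figures rest on assumed respondent numbers and upkeep rates, and on a lean model chosen for illustration. If adherence has three levels instead of four, each model has one parameter fewer and the difference of 6 between categorised and linear is unchanged.

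The weakness bears mainly on the adherence analysis and the other non-randomised comparisons. It matters less for SLH versus PExT, where the groups were formed by randomisation. Nothing here is a contradiction or an arithmetic error, and it would not by itself overturn a result.

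**What to change.** In the paragraph on modified variables, state that age, FEV1% predicted and baseline 6MWD enter all adjusted logistic models as continuous terms. Name one form before the follow-up data are merged with the RCT dataset (planned for July 2023): either linear, or restricted cubic splines with 3 knots at stated percentiles. Do not leave the choice to how the fitted data look. State that quartiles and GOLD classes are for descriptive tables only.

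The cost is SAP wording. Age, lung function and walking distance were already collected in the RCT, so no new data are needed. Coefficients will be read per unit (or per stated increment) rather than per class. Linear terms assume linearity on the log-odds scale; the spline form relaxes this for 3 more parameters across the three variables.

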2. Whether short-term follow-up scoring values in QoL, anxiety, depression, and dyspnoea sustains at long-term follow-up. We hypothesise that SLH is non-inferior to PExT regarding sustaining of scoring and effect demonstrated in *Sing-a-Lung 1.0*.

Secondary study outcomes, and hypotheses:

- A. Whether short-term achievement of effect in QoL – defined as achievement of MID or not in SGRQ – is associated with upkeep of activity and scoring values. We hypothesise that those who achieved MID are more likely to maintain/upkeep or seek out an activity and keep up scoring values.
- B. Whether self-reported long-term level of overall physical and social activity is associated with RCT randomisation, hypothesising that SLH is non-inferior to PExT.

Whether RCT randomisation is associated with self-reported satisfaction with intervention, experienced relevance, and experienced integration of the tools obtained, hypothesising that SLH is non-inferior to PExT.

C. Whether availability of a local, structured upkeep course in physical training or a lung choir is correlated to long-term upkeep of activity, hypothesising that available local, structured offer improves likelihood of upkeep of activity. Furthermore, we hypothesise that SLH is non-inferior to PExT regarding likelihood of upkeep of activity.

Design Plan

Study type

The present study is an observational study, based on a follow-up study in the RCT cohort of *Sing-a-Lung 1.0* (n=270) (Trial registration number: NCT03280355; project title: “The Effects of Singing Training for Patients with Chronic Obstructive Pulmonary Disease (COPD)”).

Blinding

The research assistant responsible for data collection is blinded to RCT randomisation. After the analysis process, blinded results (presented as A: Level of adherence 0 compared to Level of adherence 1; and B: Treatment 0 compared to Treatment 1) will be presented to the research group, who will interpret the blinded results. Prior to unblinding of the trial results, the research group will prepare two alternative conclusions for Level of adherence and two alternative conclusions for randomisation.⁹

Study design

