The present study is a long-term follow-up study of upkeep of activity and sustaining of effects across RCT study groups in *Sing-a-Lung 1.0* (SLH and PExT) using validated and specially developed questionnaires to facilitate descriptive and comparative analyses and to conduct mixed-methods inspired research equivalent to our previously published, survey-based research. The validated questionnaires cover QoL, dyspnoea, and symptoms of anxiety and depression, and are all specifically validated and used for COPD. The specially developed questionnaires were developed by PostDoc, Ph.d., [name] in close collaboration with Ph.d., Consultant in Pulmonology, [name], and discussed and settled with the additional research group members: Professor, Ph.d., Consultant in Pulmonology, [name]; Professor, D.MS.c, Consultant in Pulmonology, [name]; and Associate Professor, D.MS.c, Consultant in Pulmonology, [name].

Randomisation

Participants were randomised during the *Sing-a-Lung 1.0* RCT (Trial registration number: NCT03280355). The intervention phase of *Sing-a-Lung 1.0* took place between August 2017 and May 2019.

Sampling Plan

Existing Data

Already collected data from *Sing-a-Lung 1.0* include:

- Basic baseline characteristics: *e.g.* age, BMI, socio-demographics, smoking history, health care utilisation, exacerbations, medicine, comorbidities, and expectations towards benefits of singing.
- Baseline and short-term follow-up data related to *Sing-a-Lung 1.0* outcomes: Physical Capacity (Six-Minutes Walking Test; 6MWT), Quality of Life (St Georges' Respiratory Questionnaire; SGRQ), anxiety and depression (Hospital Anxiety and Depression Scale; HADS), dyspnoea (BORG-CR10 and Modified Medical Research Scale, mMRC), lung function (Forced Expiratory Volume in one Second; FEV1% predicted and Forced Vital Capacity; FVC% predicted), respiratory muscle strength and control (inspiratory pressure, breath counting scale, breath holding test), adherence, drop-out-rate, medicine consumption, number of COPD-related hospitalisations and exacerbations, and satisfaction with study intervention.

Sample size

RCT cohort of *Sing-a-Lung 1.0* (n=270). Participants who accept to participate will be included in the study. The following participants will be excluded from analyses: 1) Do not accept to participate, 2) Not reachable via telephone (after three attempts at different dates), 3) Deceased since *Sing-a-Lung 1.0*.

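### Hypothesis A uses achievement of the SGRQ MID as exposure, but baseline SGRQ is not among the variables named for the logistic models, so residual confounding by baseline symptom burden is possible

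*SAP*

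**What the plan says.** Under *Secondary study outcomes, and hypotheses*, item A, the SAP asks: "Whether short-term achievement of effect in QoL – defined as achievement of MID or not in SGRQ – is associated with upkeep of activity and scoring values". The expected direction is given next: "We hypothesise that those who achieved MID are more likely to maintain/upkeep or seek out an activity and keep up scoring values".

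Under *Analysis Plan*, the paragraph on modifications of variables defines the exposure as "Achievement of MID in RCT (SGRQ and 6MWD) or not". The SGRQ threshold there is 4 units. The patient baselines in the same paragraph are age in quartiles, FEV1% predicted by GOLD class, and "Baseline 6MWD categorised into quartiles". The other entries are adherence, randomisation, sustaining of effects and available offer. Baseline SGRQ does not appear.

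*Data analysis procedures* points to this paragraph under the label "Modifications of specific variables of interest to be included in the logistic regression models". *Statistical models* promises both adjusted and unadjusted logistic models but assigns no covariates to any hypothesis.

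Baseline SGRQ is available. *Existing Data* has an entry that begins "Baseline and short-term follow-up data related to" the RCT outcomes, and SGRQ is one of those it lists.

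**The concern.** The exposure is a change score cut at a threshold, so it depends on where the patient started. A patient with a poor baseline SGRQ has more room to improve and gains more from regression to the mean, and so may reach a 4-unit improvement more often. If that patient is also less likely to keep up an activity years later, baseline SGRQ acts on both exposure and outcome. Part of its effect would then be credited to MID achievement, against the direction that hypothesis A expects. A real association could look weaker than it is or be reported as absent.

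The list is also uneven. It names MID achievement for both SGRQ and 6MWD but supplies the starting value of 6MWD only. SGRQ, the one measure that hypothesis A names as exposure, lacks its own starting value.

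**Working it through.** **No figure to reproduce.** The SAP gives no effect size, SD or power for hypothesis A. The check is a comparison of the text, followed by illustrative simulation.

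**Text.** Exposure: SGRQ MID achieved in the RCT (hypothesis A). Baselines named for the models: age, FEV1% predicted, 6MWD. Held but not named: baseline SGRQ.

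**Simulation 1, true association present.** Let S be standardised baseline SGRQ (higher is worse), D the change in SGRQ, and M = 1 if the MID is reached.

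- corr(S, D) = r
- logit P(upkeep) = a + ln(1.8)·M + g·S

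Inputs, all assumed except where noted:

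- Share reaching the MID: 49%. The SAP reports this for the singing arm; using it for the whole cohort is an assumption.
- True conditional odds ratio: 1.8.
- r from -0.2 to -0.4; g from -0.3 to -0.7 per SD of S.
- FEV1 and 6MWD: each correlated 0.3 to 0.5 in size with S, entered as categories.

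Odds ratio for M over the whole grid:

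| Model | Odds ratio |
|---|---|
| No severity covariate | 1.13 to 1.63 |
| FEV1 and 6MWD | about 1.19 to 1.67 |
| FEV1, 6MWD and baseline SGRQ | 1.78 to 1.82 |

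The mildest corner (r = -0.2, g = -0.3) gives the upper ends of the first two rows. The most extreme corner (r = -0.4, g = -0.7) gives the lower ends.

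On the log scale ln 1.8 = 0.588, ln 1.67 = 0.513 and ln 1.19 = 0.174. With FEV1 and 6MWD in the model, the attenuation therefore runs from 1 - 0.513/0.588 = 13% to 1 - 0.174/0.588 = 70%.

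*Non-collapsibility.* With r = 0 there is no confounding, yet g = -0.7 alone gives a crude odds ratio of 1.70 against 1.81 with S in the model. So a small part of each gap is not bias.

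**Simulation 2, no true association (odds ratio 1.00).** Assumed: baseline SD 15, mean change -3, residual SD of change 10, odds ratio for activity 0.67 or 0.5 per SD of worse baseline, and FEV1 and 6MWD each correlated 0.3 or 0.5 in size with SGRQ, in quartiles.

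| Slope of change on baseline | Crude | FEV1 and 6MWD | Plus baseline SGRQ |
|---|---|---|---|
| 0 | 1.00 to 1.01 | 1.00 to 1.01 | 1.00 to 1.01 |
| -0.1 | 0.87 to 0.91 | 0.89 to 0.94 | 1.00 to 1.01 |
| -0.2 | 0.75 to 0.84 | 0.78 to 0.89 | 0.97 to 1.01 |
| -0.3 | 0.66 to 0.76 | 0.70 to 0.83 | 0.98 to 1.02 |

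At slope -0.3 about 25% of the best baseline quartile and 68% of the worst reach the MID. The two listed severity measures remove only a minority of the bias. For example, moving from 0.66 to 0.70 removes 1 - ln 0.70/ln 0.66 = 1 - 0.357/0.416 = 14%, and moving from 0.67 to 0.77 removes 1 - 0.261/0.400 = 35%.

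**The case against.** **The list may not be the adjustment set.** Most entries are recodings into classes, quartiles or yes/no, and a continuous baseline score needs none. BMI and smoking history are also held and also absent. A reader might infer that the SAP rules out baseline SGRQ. It does not, because the list is nowhere called exhaustive and no final model is written down. This stands in part. Still, *Data analysis procedures* describes these as variables to be included in the models, and randomisation is listed although it needs no recoding. This is the only list tied to the logistic models, and baseline SGRQ is not in it.

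**Severity is partly covered.** A reader might infer that the comparison is confounded by how ill patients were at the start. That is too strong, since FEV1 by GOLD class and baseline 6MWD are both listed. What can remain is confounding by baseline symptom burden. For the same reason 1.13 to 1.63 is not the right measure of the problem, since it comes from a model with neither variable.

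**Size and direction are assumed.** This stands fully. No passage shows that worse baseline SGRQ goes with less activity later. The activity outcome also includes singing, other musical or creative pursuits, and self-rated activity compared with before the intervention. For these a negative link is not established.

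**The question may be prognostic.** Hypothesis A asks about association. If the aim is only to say whether achievers go on to be more active, the unadjusted odds ratio is a legitimate answer. This stands, and is why the unadjusted model should be kept. It does not help the adjusted model, which needs the starting value of its own exposure.

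**Conclusion.** The point holds as possible residual confounding in one secondary hypothesis. The SAP holds baseline SGRQ, uses change from it as the exposure, and does not name it for the adjusted models, although it names the walk-test baseline.

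Under the stated assumptions, a true odds ratio of 1.8 would appear as about 1.19 to 1.67 after adjustment for FEV1 and 6MWD, and as about 1.8 with baseline SGRQ added. The pull toward no effect needs both links: worse baseline SGRQ with more frequent MID achievement, and with less later activity. If either is zero, there is no confounding.

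A reader might also infer that the primary outcome or the comparison of singing with exercise training is affected. The documents do not support that, because the point concerns only models of upkeep with SGRQ MID achievement as exposure. The calculations do not cover the part of hypothesis A that deals with long-term scores.

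The change is worth making because it is specific and nearly free. Confidence is medium, since the size cannot be derived from the documents.

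**What to change.** Add baseline SGRQ, as a continuous variable, to the list of model variables in the *Analysis Plan*. State that it enters every adjusted logistic model of upkeep in which SGRQ MID achievement is the exposure. Keep the planned unadjusted model and label it as the descriptive association.

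The cost is one model parameter and one line of SAP text. The data are already held, and nothing changes in data collection.

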Add-on to NCT03280355

Statistical Analysis Plan for a long-term follow-up study in RCT “The Effects of Singing Training for Patients with Chronic Obstructive Pulmonary Disease (COPD)” (NCT03280355).

Document date: 06/19/2023

Title of follow-up study:

Long-term upkeep of activity, effects, and impact following pulmonary rehabilitation for COPD with either Singing for Lung Health or physical exercise training.

Study Information

In our recent multicentre RCT - *Sing-a-Lung 1.0* - comparing Singing for Lung Health (SLH) with usual-care physical exercise training (PExT) within 10 week's community-based pulmonary rehabilitation (PR) for COPD (NCT03280355), we demonstrated that SLH conferred relevant short-term improvements regarding both physiological and psychological parameters and was non-inferior to PExT.¹⁻³ Post-hoc analyses demonstrated that effect was correlated with adherence in both groups,⁴ and, moreover, suggested that SLH was associated with improved inspiratory muscle control and dyspnoea control, and that a larger proportion in SLH achieved the minimal important difference (MID) in quality of life (QoL) (measured by change in St George's Respiratory Questionnaire; SGRQ; MID = ≤ 4 units) than in physical capacity (measured by change in 6-Minute Walk Test Distance; 6MWD; MID = ≥ 30 m) (49% vs. 29%).⁵

Little is, however, known about the long-term effects of SLH including upkeep of activity, effects, and life-style changes, which is a well-known significant challenge within PR with PExT.⁶⁻⁸

Aims and hypotheses

With the present project - *Sing-a-Lung 1.1* - we will conduct a long-term follow-up study within the study cohort of *Sing-a-Lung 1.0* (n=270; SLH n=145/PExT=125) to investigate long-term upkeep of activity. Secondarily, we will investigate sustainability of effect and impact on quality of life, anxiety, depression, and dyspnoea. Furthermore, we aim to obtain deeper insight into how the study participants have integrated the tools derived from participating in either SLH or PExT.

Specifically, we aim to investigate:

Primary study outcome and hypotheses:

1. Whether level of adherence demonstrated in *Sing-a-Lung 1.0* is correlated with upkeep of activity. We hypothesise that high adherence in *Sing-a-Lung 1.0* predicts high long-term upkeep of activity after *Sing-a-Lung 1.0* and vice versa for low adherence. Moreover, we hypothesise that SLH is non-inferior to PExT in upkeeping long-term activity.

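### Six hypotheses stand under the primary heading at an unadjusted p < 0.05, although the SAP elsewhere makes four of them secondary

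*SAP*

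**What the plan says.** **Primary heading.** Under Primary study outcome and hypotheses, item 1 carries two claims. The first concerns whether adherence in the original trial "is correlated with upkeep of activity. We hypothesise that high adherence in" that trial predicts high upkeep. The second reads "Moreover, we hypothesise that SLH is non-inferior to PExT in upkeeping long-term activity". Item 2 asks "Whether short-term follow-up scoring values in QoL, anxiety, depression, and dyspnoea sustains at long-term follow-up" and adds "We hypothesise that SLH is non-inferior to PExT regarding sustaining of scoring and effect demonstrated in" the original trial. Item 2 therefore covers four domains, and the heading holds 2 + 4 = 6 hypotheses.

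**Status of item 2.** The opening of Aims and hypotheses says "Secondarily, we will investigate sustainability of effect and impact on quality of life, anxiety, depression, and dyspnoea". The outcome table under Measured variables agrees: upkeep is its only primary row, and the four scores stand under the secondary outcomes.

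**Secondary heading.** Hypothesis A says "We hypothesise that those who achieved MID are more likely to maintain/upkeep or seek out an activity and keep up scoring values". Hypothesis B, an unlettered paragraph on satisfaction, relevance and tools, and hypothesis C follow.

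**Error rule.** The Analysis Plan gives one: "Statistical significance will be reported as $p < 0.05". It does not state sidedness. It speaks of exploring interactions and baseline characteristics, but does not call any listed hypothesis exploratory.

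**The concern.** A primary heading tells readers which results carry the study's conclusion. Here it holds six directional claims, five of them SLH-versus-PExT non-inferiority claims, and each may be declared at the full threshold. The plan does not say whether item 2 needs all four scores or any one of them. As written, nothing prevents one favourable score from being reported as a primary non-inferiority result when the upkeep comparison fails.

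The contradiction over item 2 makes this worse. After the results are known, the same four scores could be called primary or secondary, and the text would support either.

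**Working it through.** The SAP states no familywise error rate, so there is no figure of its own to reproduce.

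**Inputs from the SAP**
- Threshold: 0.05 per test, sidedness not stated.
- Primary heading: 6 hypotheses (1 on adherence, 5 on arms).
- Primary hypotheses if item 2 is secondary: 2.
- Secondary heading: A 5 (upkeep and four scores) + B 1 or 2 (physical and social activity together or apart) + satisfaction, relevance and tools 3 + C 2 = 11 or 12.

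**Assumptions (not in the SAP)**
- The five arm tests share a common correlation of 0 to 0.7.
- The adherence test is independent of them.
- Upkeep is a single variable.
- Every null hypothesis is true at its boundary.

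**Six primary hypotheses.** Let F be the chance of at least one false claim among the five arm tests. For independent tests at level a, F = 1 − (1 − a)^5. For correlated tests, F comes from an equicorrelated multivariate normal. Adding the adherence test at level b gives 1 − (1 − F)(1 − b).

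| Arm tests; adherence test | Correlation 0 | 0.5 | 0.7 |
|---|---|---|---|
| F, one-sided 5% | 22.62% | 16.63% | 13.50% |
| with adherence at 5% | 26.5% | 20.8% | 17.8% |
| F, one-sided 2.5% | 11.89% | 9.15% | 7.42% |
| with adherence at 5% | 16.3% | 13.7% | 12.0% |
| with adherence counted in the claimed direction only, 2.5% | 14.1% | 11.4% | 9.7% |

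Upper end: 1 − (1 − 0.2262) × 0.95 = 26.5%. Lower end: 1 − (1 − 0.0742) × 0.975 = 9.7%. The range is therefore about 10-27%. If the adherence test were also correlated at 0.7 with the other five, the lower end would be 8.2%.

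**Two primary hypotheses (independent)**
- Both at 5%: 1 − 0.95² = 9.75%.
- One at 5%, one at 2.5%: 1 − 0.95 × 0.975 = 7.4%.
- Both at 2.5%, counted in the claimed direction: 1 − 0.975² = 4.9%.

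The range is about 5-10%. Positive correlation between the two would lower these figures a little.

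**Item 2 read as one claim needing all four scores.** Such a claim has error of at most the per-test level. Three claims then remain, with at most 1 − 0.95³ = 14.3% if independent.

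**Effect of sharing alpha.** Two tests at 0.025 each give at most 0.025 + 0.025 = 5%.

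**The case against.** The strongest reply is that item 2 is secondary in two of the three places that classify it. On that reading only two primary tests remain, and the inflation is modest. This stands. The six-test range applies only to the hypothesis list as written. At the lowest two-test figure, 4.9%, the familywise rate does not exceed 5%, although it is about twice the 2.5% level that each claim then carries.

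A second reply is that the study is observational, is to be reported under STROBE, and never calls itself confirmatory. That is true. But directional non-inferiority hypotheses under a primary heading, with a significance threshold, will be read as claims unless the SAP labels them otherwise.

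Three stronger readings are tempting, and the SAP does not support them:
- **A single inflation figure.** Any one percentage requires a chosen correlation and sidedness, and the SAP gives neither. Counting two-sided rejections would also include results showing SLH to be worse, which are not false non-inferiority claims.
- **A defect in the blinded interpretation.** The Blinding section says "the research group will prepare two alternative conclusions for Level of adherence and two alternative conclusions for randomisation". A reader might infer that five arm comparisons are forced into one verdict with no rule for choosing it. But these conclusions are written after the blinded results have been interpreted and before unblinding. The natural reading is one conclusion per possible code assignment, and each can describe mixed results.
- **A familywise rate over all primary and secondary tests.** Hypothesis C repeats the SLH-versus-PExT upkeep claim, and the activity level in B is also among the listed measures of upkeep. Adding everything up counts the same claims twice.

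**Conclusion.** The point holds in limited form. The SAP contradicts itself on whether the four scores are primary, and it applies one unadjusted threshold to every hypothesis, with no rule for sharing error among the primary ones. The chance of at least one false primary claim is about 10-27% if all six are primary and about 5-10% if only the two upkeep hypotheses are. Both ranges rest on the assumptions listed in the working, above all correlation, sidedness and a single upkeep variable. Which range applies cannot be settled until the SAP resolves the status of item 2. This should be corrected, and it is a matter of wording.

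**What to change.** Before the July 2023 merge, amend the SAP as follows:

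1. Make the two upkeep hypotheses (adherence, and SLH versus PExT) the only primary tests, in line with the SAP's own outcome table. Move item 2 to the secondary heading.
2. Share alpha between the two, either by Holm (smaller p-value against 0.025 and, if that is met, the other against 0.05) or at 0.025 each. Do not gate one behind the other, since they answer different questions. State the sidedness. With two-sided 0.025, the non-inferiority conclusion is read from a 97.5% confidence interval.
3. Report SGRQ, HADS anxiety, HADS depression, mMRC, hypotheses A to C and the satisfaction, relevance and tools comparisons as estimates with 95% confidence intervals. Label them supportive or exploratory, with no claim of significance or non-inferiority.
4. Delete the repeated SLH-versus-PExT upkeep claim from hypothesis C.

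The primary non-inferiority test also needs a single upkeep variable and a margin.

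The cost is a paragraph of text and no new data. The study gives up any confirmatory claim on the scores, and the two upkeep tests lose some power. For a test assumed to have 80% power at two-sided 0.05, power at 0.025 is Φ(1.960 + 0.842 − 2.241) = Φ(0.560), about 71%. Holm recovers part of that loss.
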